5.5.1 Primary Efficacy Analysis

The primary efficacy endpoint is change from baseline to Visit 3/Month 2 in overall LFGS. The null hypothesis to be tested is that the Test device is inferior to the Control device. The results for PP are considered as definitive and those for mITT as supportive.

Summary statistics (mean, SD, minimum, median, maximum) and 95% confidence interval (CI) for mean will be presented for the changes scores for each treatment.

Due to the fact that the change scores would only contain 5 possible values (0, 1, 2, 3, and 4), the normal distribution assumption is hardly attainable, and therefore, the nonparametric Hodges-Lehmann (HL) estimators will be employed to test the study hypothesis. The 95% confidence limits for the median differences between the two treatment groups (PN40082 minus Restylane Silk) will be derived using PROC NPARIWAY with the option for the HL estimators. If the lower limit is on or above -1.0, the null hypothesis will be rejected to support the claim that PN40082 is non-inferior to Restylane Silk.

For the mITT analysis, the above analysis will be carried out for each copy of the MI data sets. Then PROC MIANALYZE will be performed to account for the between and within variation in the multiply imputed data sets.

To assist an assessment for the consistency of the treatment effect among sites, summary of the primary endpoint will be presented by site for the primary population (i.e., the PP subjects).

The primary endpoint will also be analyzed for the following two subsets of the PP subjects: (1) subjects that have injection on one lip only, and (2) subjects that have injections on both lips.

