5.5.2 Secondary Efficacy Analysis

The secondary efficacy endpoints include the following:

- percent of subjects with treatment success (responder on overall LFGS) at Visit 3/Month 2, where responder is defined as a subject with at least a 1-grade increase from baseline on the overall LFGS
- percent of responders on the overall POL severity scale at Visit 4/Month 3 (defined as a subject demonstrating ≥ 1 -point improvement, i.e., decrease in severity, from baseline)
- change from baseline to Visit 4/Month 3 in overall LFGS
- change from baseline to Visit 5/Month 6 in overall LFGS

The supporting importance of the secondary endpoints is ordered by [1] percent of subject with treatment success (responder on overall LFGS) at Visit 3/Month 2, [2] percent of responders on the overall POL severity scale at Visit 4/Month 3, [3] change from baseline to Visit 4/Month 3 in overall LFGS, and [4] change from baseline to Visit 5/Month 6 in overall LFGS.

These secondary variables will be summarized with descriptive statistics for each treatment arm and a 95% CI for the difference between treatments. For the proportion variables, the 95% CI for treatment difference will be calculated using the Wald's method, with subjects pooled from all study sites. For the change variables, the 95% CI for the median differences between treatments will be derived using PROC NPARIWAY with the option for the HL estimators.

For the mITT analysis, the LFGS-related secondary endpoints will be analyzed for each copy of the MI data sets. PROC MIANALYZE will then be performed to account for the between and within variation in the multiply imputed data sets.

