O:\Studies\Prollenium\SYM 2018-02\Biometrics\Programs\Tables\xxx.sas ran on Month Day, Year at hh:mm on data from Month Day, Year.

Table 14.2.1.1 – Primary Analysis of Primary Efficacy Endpoint for Per-Protocol Population: Change from Baseline to Visit 3/Month 2 in Overall Lip Fullness Grading Scale (LFGS)

Population	Statistics	PN40082	Restylane Silk
Per-Protocol (PP)	N	0	0
	Mean ± SD	0.0 ± 0.00	0.0 ± 0.00
	95% CI of Mean	(0.00, 0.00)	(0.00, 0.00)
	Median	0.0	0.0
	Min, Max	0, 0	0, 0
	Median Differences and 95% Confidence Limits for PN40082 minus Restylane Silk	0.0 (0.0, 0.0) [†]	

LFGS: 0=Very Thin Lips, 1=Thin Lips, 2=Moderately Thick Lips, 3=Thick Lips, 4=Full Lips.

[†]Median differences and 95% confidence limits are derived using Hodges-Lehmann estimators from PROC NPAR1WAY.

Source: Listing 16.2.6.2.3

O:\Studies\Prolenium\SYM 2018-02\Biometrics\Programs\Tables\xxx.sas ran on Month Day, Year at hh:mm on data from Month, Day, Year.

Table 14.2.1.2 – Supportive Analysis of Primary Efficacy Endpoint for Modified Intent-to-Treat Population: Change from Baseline to Visit 3/Month 2 in Overall Lip Fullness Grading Scale (LFGS)

Imputation Date Set	Statistics	PN40082	Restylane Silk
Data Set #1	N	0	0
	Mean ± SD	0.0 ± 0.00	0.0 ± 0.00
	95% CI of Mean	(0.00, 0.00)	(0.00, 0.00)
	Median	0.0	0.0
	Min, Max	0, 0	0, 0
	Median Differences and 95% Confidence Limits for PN40082 minus Restylane Silk	0.0 (0.0, 0.0) ¹	
Data Set #2			
...			
Data Set #5	Mean ± SD	0.0 ± 0.00	0.0 ± 0.00
	95% CI of Mean	(0.00, 0.00)	(0.00, 0.00)
	Median	0.0	0.0
	Min, Max	0, 0	0, 0
	Median Differences and 95% Confidence Limits for PN40082 minus Restylane Silk	0.0 (0.0, 0.0) ¹	
Combined Analysis	Median Differences and 95% Confidence Limits for PN40082 minus Restylane Silk	0.0 (0.0, 0.0) ²	

LFGS: 0=Very Thin Lips, 1=Thin Lips, 2=Moderately Thick Lips, 3=Thick Lips, 4=Full Lips.

For the mITT analysis, missing overall LFGS scores will be replaced using the multiple imputation (MI) approach.

¹Median differences and 95% confidence limits are derived using Hodges-Lehmann estimators from PROC NPARIWAY.

²Median differences and 95% confidence limits for combined analysis are derived from PROC MIANALYZE.

Source: Listing 16.2.6.2.2

O:\Studies\Prolenium\SYM 2018-02\Biometrics\Programs\Tables\cxxx.sas ran on Month Day, Year at hh:mm on data from Month, Day, Year.

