Source: Listing 16.2.6.2.2, 16.2.6.2.3

O:\Studies\Prolenium\SYM 2018-02\Biometrics\Programs\Tables\xxx.sas ran on Month Day, Year at hh:mm on data from Month, Day, Year.

Table 14.2.3.6 – Other Efficacy: Subject Satisfaction with Lips VAS by Visit Based on Observed Data

Study Visit	Category	Modified Intent-to-Treat		Per-Protocol	
		PN40082	Restylane Silk	PN40082	Restylane Silk
Visit 2/Month 1	N	0	0	0	0
	Mean ± SD	0.0 ± 0.00	0.0 ± 0.00	0.0 ± 0.00	0.0 ± 0.00
	Median	0.0	0.0	0.0	0.0
	Min, Max	0, 0	0, 0	0, 0	0, 0
Visit 3/Month 2					
...					
Visit 5/Month 6	N	0	0	0	0
	Mean ± SD	0.0 ± 0.00	0.0 ± 0.00	0.0 ± 0.00	0.0 ± 0.00
	Median	0.0	0.0	0.0	0.0
	Min, Max	0, 0	0, 0	0, 0	0, 0

Source: Listing 16.2.6.1.3

O:\Studies\Prolenium\SYM 2018-02\Biometrics\Programs\Tables\xxx.sas ran on Month Day, Year at hh mm on data from Month, Day, Year.

Table 14.2.3.7 – Other Efficacy: Change from Baseline to Visit 4/Month 3 and Visit 5/Month 6 in Lip Fullness Grading Scale (LFGS) for Upper Lips and Lower Lips
Based on Observed Data

Population	Visit	Category	Upper Lips		Lower Lip	
			PN40082	Restylane Silk	PN40082	Restylane Silk
Per-Protocol	Visit 4/Month 3	N	0	0	0	0
		Mean ± SD	0.0 ± 0.00	0.0 ± 0.00	0.0 ± 0.00	0.0 ± 0.00
		Median	0.0	0.0	0.0	0.0
		Min, Max	0, 0	0, 0	0, 0	0, 0
	Visit 5/Month 6	N	0	0	0	0
		Mean ± SD	0.0 ± 0.00	0.0 ± 0.00	0.0 ± 0.00	0.0 ± 0.00
		Median	0.0	0.0	0.0	0.0
		Min, Max	0, 0	0, 0	0, 0	0, 0
Modified Intent-to-Treat	Visit 4/Month 3	N	0	0	0	0
		Mean ± SD	0.0 ± 0.00	0.0 ± 0.00	0.0 ± 0.00	0.0 ± 0.00
		Median	0.0	0.0	0.0	0.0
		Min, Max	0, 0	0, 0	0, 0	0, 0
	Visit 5/Month 6	N	0	0	0	0
		Mean ± SD	0.0 ± 0.00	0.0 ± 0.00	0.0 ± 0.00	0.0 ± 0.00
		Median	0.0	0.0	0.0	0.0
		Min, Max	0, 0	0, 0	0, 0	0, 0

Source: Listing 16.2.6.2.4

O:\Studies\Prollenium\SYM 2018-02\Biometrics\Programs\Tables\xxx.sas ran on Month Day, Year at hh mm on data from Month, Day, Year.

Table 14.3.1.1 – Exposure to Study Product and Investigator Ease of Use Assessment (Upper Lips) at Visit 1/Day 1 and Visit 2/Month 1 for As-Treated Population

	Statistics	Visit 1/Day 1		Visit 2/Month 1	
		PN40082	Restylane Silk	PN40082	Restylane Silk
Amount of Syringe Used (ml)	N	0	0	0	0
	Mean ± SD	0.0 ± 0.00	0.0 ± 0.00	0.0 ± 0.00	0.0 ± 0.00
	Median	0.0	0.0	0.0	0.0
	Min, Max	0, 0	0, 0	0, 0	0, 0
Injection Techniques Used	N (%) Serial Puncture	0 (0.0%)	0 (0.0%)	0 (0.0%)	0 (0.0%)
	N (%) Antegrade Linear Threading	0 (0.0%)	0 (0.0%)	0 (0.0%)	0 (0.0%)

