Site- Subject	Analyses	Study Visit	Subject	Swelling Assessment		Patient Global Aesthetic	Investigator Global Aesthetic Improvement	
			Satisfaction with Lips VAS	Grade	Performed By	Improvement (pGAI)	Score	(iGAI) Performed By
Treatment:								

Analyses: A = As-Treated (AT) Analyses, M = Modified Intent-to-Treat (MITT) Analyses, P = Per-Protocol Analyses

O:\Studies\ Prolenium\SYM 2018-02\Biometrics\Programs\Listing\xxx.sas ran on Month Day Year at hh mm on data from Month Day, Year.

Listing 16.2.6.2.1 – Derived Overall Lip Fullness Grading Scale (LFGS) for Modified Intent-to-Treat Population

Site-Subject	Fitzpatrick skin type	Lips Treated	Visit 1	Visit 2	Visit 3	Visit 4	Visit 5
Treatment: XX-XXX	II	Both	1	2	3	2	2, 3, 2, 2, 3

LFGS: 0=Very Thin Lips, 1=Thin Lips, 2=Moderately Thick Lips, 3=Thick Lips, 4=Full Lips.

Note: The 5 entries contained under a visit for a subject are the 5 imputed LFGS scores for the missing value through multiple imputations.

O:\Studies\ Prollenium\SYM 2018-02\Biometrics\Programs\Listing\xxx.sas ran on Month Day Year at hh mm on data from Month Day, Year.

Listing 16.2.6.2.2 – Derived Primary and Secondary Efficacy Responses on Overall LFGS and Overall POL for Modified Intent-to-Treat Population

Site-Subject	Study Visit	Lip Fullness Grading Scale (LFGS)			Perioral Lines at Rest Severity Scale (POL)		
		Overall LFGS Rating	Change from Baseline	Treatment Success [†]	Overall POL Rating	Change from Baseline	Responder ^{**}
Treatment:							
XX-XXX	4	2	-1	Y			
	5	2, 3, 2, 2, 3	-1, -2, -1, -1, -2	Y, Y, Y, Y, Y			

Change from Baseline for Visit x = Baseline – Visit x, where x=2, 3, 4, 5.

[†]Treatment success is defined as an achievement of at least a 1-grade increase from baseline on the overall LFGS.

^{**}Responder is defined as a subject demonstrating at least 1-point improvement, i.e., decrease in severity, from baseline POL severity.

Note: The 5 entries contained under a visit for a subject are associated the 5 imputed LFGS scores for the missing value through multiple imputations.

O:\Studies\ Prolenium\SYM 2018-02\Biometrics\Programs\Listing\cxc.sas ran on Month Day Year at hh mm on data from Month Day, Year.

Listing 16.2.6.2.3 – Derived Primary and Secondary Efficacy Responses on Overall LFGS and Overall POL for Per-Protocol Population

Site-Subject	Study Visit	Lip Fullness Grading Scale (LFGS)			Perioral Lines at Rest Severity Scale (POL)		

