		Overall LFGS Rating	Change from Baseline	Treatment Success*	Overall POL Rating	Change from Baseline	Responder**
Treatment:							

Change from Baseline for Visit x = Baseline – Visit x, where x=2, 3, 4, 5.

*Treatment success is defined as an achievement of at least a 1-grade increase from baseline on the overall LFGS.

**Responder is defined as a subject demonstrating at least 1-point improvement, i.e., decrease in severity, from baseline POL severity.

O:\Studies\Prolenium\SYM 2018-02\Biometrics\Programs\Listing\xxx.sas ran on Month Day Year at hh mm on data from Month Day, Year.

Listing 16.2.6.2.4 – Derived Other Efficacy Responses Based on Observed Data: LFGS and POL for Upper/Lower Lip

Site- Subject	Analyses	Study Visit	Upper or Lower Lip	Lip Fullness Grading Scale (LFGS)			Perioral Lines at Rest Severity Scale (POL)		
				LFGS Rating	Change from Baseline	Treatment Success*	POL Rating	Change from Baseline	Responder**
Treatment:									

Change from Baseline for Visit x = Baseline – Visit x, where x=2, 3, 4, 5.

*Treatment success is defined as an achievement of at least a 1-grade increase from baseline on the overall LFGS.

**Responder is defined as a subject demonstrating at least 1-point improvement, i.e., decrease in severity, from baseline POL severity.

O:\Studies\Prolenium\SYM 2018-02\Biometrics\Programs\Listing\xxx.sas ran on Month Day Year at hh mm on data from Month Day, Year.

Listing 16.2.7.1.1 – Adverse Events (Related to Vascular Injections/Visual Events)

Site- Subject	Analy	FST	Reported by	System Organ Class// Preferred Term// Verbatim Term	Start Date Time [Day #]	Stop Date Time [Day #]	Severity Causality Outcome	Where on face Rel. to injection? Vision related?	Action Taken ¹	SAE
Treatment:										
xx-xxx	A	III	Subj/Diary	GENERAL DISORDERS AND ADMINISTRATION	01JAN2019	04JAN2019	MILD	QD1, QD3	3,4	N
				SITE CONDITIONS//						
				INJECTION SITE SWELLING//	13:25	08:30	PROBABLY	Y		
				SWELLING ON FACE	2	5	STABLIZED	N		

Analy (Analyses): A = As-Treated (AT) Analyses only, M = Modified Intent-to-Treat (MITT) Analyses, P = Per-Protocol Analyses

Day # is calculated from baseline (Visit 1) date. Day 1 is the baseline date while Day -1 is the day prior to the baseline visit.

¹ Action Taken: 1=None, 2=Study treatment interrupted/discontinued, 3=Non-drug therapy, 4=New OTC or Rx drug added, 4=Hospitalized

O:\Studies\ Prolenium\SYM 2018-02\Biometrics\Programs\Listing\xxx.sas ran on Month Day Year at hh mm on data from Month Day, Year.

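### The SAP's only written formula for LFGS change, in the footnotes to Listings 16.2.6.2.2 to 16.2.6.2.4, has the opposite sign to the one its section 5.5.1 non-inferiority rule needs

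*SAP*

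**What the plan says.** Three listing shells in the SAP carry the same footnote: 16.2.6.2.2 (mITT, overall scores), 16.2.6.2.3 (PP, overall scores) and 16.2.6.2.4 (upper and lower lip). It reads "Change from Baseline for Visit x = Baseline – Visit x, where x=2, 3, 4, 5". Each shell covers both LFGS and POL. Each also says, for LFGS, "Treatment success is defined as an achievement of at least a 1-grade increase from baseline on the overall LFGS".

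Listing 16.2.6.2.2 contains a filled-in LFGS example. It prints a change of -1 at Visit 4 and -1, -2, -1, -1, -2 at Visit 5, every entry marked as a success.

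SAP 5.5.1 gives no formula for change. It says that "the change scores would only contain 5 possible values (0, 1, 2, 3, and 4") and sets the decision rule on PN40082 minus Restylane Silk: "If the lower limit is on or above -1.0, the null hypothesis will be rejected". SAP 5.5.2 states the responder rule in words: "responder is defined as a subject with at least a 1-grade increase from baseline on the overall LFGS". SAP 5.5 scores LFGS from 0 (very thin) to 4 (full), so a higher score is a fuller lip.

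Table 14.2.1.1 (primary, PP) carries the line "Source: Listing 16.2.6.2.3", Table 14.2.1.2 (mITT) the line "Source: Listing 16.2.6.2.2", and Table 14.2.3.7 (upper and lower lip change) the line "Source: Listing 16.2.6.2.4". SAP 6 describes the tables and listings as examples that may be changed during analysis.

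**The concern.** A lower-limit non-inferiority rule protects against an inferior test device only when larger values are better. For LFGS that means Visit minus Baseline. The only formula the SAP writes down is the reverse, and the worked example shows it was applied to LFGS on purpose, so it is not a stray typing slip. A likely cause is that one footnote serves two scales running in opposite directions: Baseline minus Visit makes improvement positive for POL and negative for LFGS.

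Nothing in the SAP says that the sign is switched before analysis. If someone programmed the analysis variable from the footnote and kept the 5.5.1 rule, the primary test would face the wrong way. If the programmer followed 5.5.1, the listings would still print signs opposite to those in the tables that name them as source.

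**Working it through.** **1. Reproduce the listing's own figures.** Listing 16.2.6.2.1 shows an example subject with Visit 1 = 1, Visit 4 = 2 and imputed Visit 5 scores 2, 3, 2, 2, 3. These ratings match the example rows in Listing 16.2.6.2.2.

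| | Visit 4 | Visit 5 |
|---|---|---|
| Baseline minus Visit | 1 - 2 = -1 | -1, -2, -1, -1, -2 |
| Visit minus Baseline | 2 - 1 = +1 | +1, +2, +1, +1, +2 |

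The first row is exactly what is printed. Only the second row fits the 0 to 4 range in 5.5.1, and only in the second row does the sign match the success flags.

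**2. What the reversed sign does to the rule.** Let L and U be the lower and upper 95% Hodges-Lehmann limits for PN40082 minus Restylane Silk, with change as Visit minus Baseline. Reversing every change score reverses every pairwise difference, so the new lower limit is -U.

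- Correct sign: pass if L ≥ -1.0.
- Reversed sign: pass if -U ≥ -1.0, that is, U ≤ +1.0.

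The second condition asks whether PN40082 is not too much better. It has no power to detect inferiority.

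**3. How far the two rules differ.**

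Inputs from the SAP: 63 PP subjects per arm and a planning SD of 0.85 (section 3.2), and the -1.0 rule (section 5.5.1). The protocol's different margin is a separate matter and is not used here.

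Assumptions, not in the documents: change is a rounded normal variable with latent SD 0.80 (realised control SD about 0.83 to 0.85) and control mean 1.5 or 2.0. Scores are either floored at 0, as 5.5.1 supposes, or allowed to fall below 0. That gives four scenarios.

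The limits are the k-th smallest and k-th largest of the 63 × 63 = 3,969 pairwise differences, where k = floor(3969/2 - 1.96 × √(3969 × 127/12)) = floor(1984.5 - 401.7) = 1582.

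Simulated pass rates over the four scenarios, rounded because independent runs differ slightly:

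| Latent shift for PN40082 | Correct sign | Reversed sign |
|---|---|---|
| within ±0.75 | at least about 99.6% | at least about 99.6% |
| 1.25 worse | about 36 to 48%; about 85% in one floored scenario | 100% |
| 1.5 worse | about 3 to 8%; about 55% in that scenario | 100% |
| 1.5 better | 100% | about 3 to 8% |

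The shifts are latent. Where scores are floored at 0, a latent -1.5 becomes a realised difference of about -1.21 (control mean 1.5) or -1.39 (control mean 2.0). The first of these is the scenario with the 55% figure; there a latent -1.25 is realised as about -1.07.

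**The case against.** The strongest reply is that the governing section already settles the sign. Baseline minus Visit would turn the scores in 5.5.1 into 0 to -4, which that section does not allow. Sections 5.5.1 and 5.5.2 therefore give a programmer one consistent reading. The conflicting footnote sits in example shells that SAP 6 lets the analysts modify. Reversed scores would also be conspicuous, because Table 14.2.1.1 prints mean, median, minimum and maximum by arm and both arms would be negative. All of this stands, and it is why the point is minor. It does not remove the error: permission to modify a shell does not correct it, and negative means would be noticed only once results exist, a poor time to change the sign of the primary variable.

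Three stronger readings are tempting, and the documents do not support them.

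- A reader might infer that the planned primary test is inverted as written. It is not, because 5.5.1 implies the correct direction.
- A reader might infer from the source lines that the listings feed the analysis. Those lines show traceability only and are not fully reliable: Table 14.2.3.4, on upper and lower lips, cites the two overall-score listings.
- A reader might infer that the secondary results are at risk too. Responder endpoints are defined in words as an increase and are unaffected. The Month 3 and Month 6 change summaries could be printed with the wrong sign, but SAP 5.1 treats the secondary comparisons as descriptive.

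**Conclusion.** The contradiction is real. The SAP's only explicit change formula, backed by a worked example, has the wrong sign for LFGS under the SAP's own primary rule. The consequence is conditional on the variable being derived from the footnote while the 5.5.1 rule stays unchanged.

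Even then, the decision hardly changes unless the arms differ by about 1 grade or more, and there is no effect at the planning assumption of equal means. Beyond that point the reversal matters: a clearly inferior device would pass and a clearly better one would fail. The direction of this effect follows from the algebra alone. The pass rates depend on the assumed control mean, latent SD and flooring, and are illustrative.

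Severity is minor.

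**What to change.** Before database lock:

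- State in SAP 5.5.1, beside the non-inferiority rule, that LFGS change is Visit x minus Baseline, so that a positive value means a fuller lip.
- Correct the footnote for LFGS in Listings 16.2.6.2.2, 16.2.6.2.3 and 16.2.6.2.4 to match.
- Change the example in Listing 16.2.6.2.2 to +1 at Visit 4 and +1, +2, +1, +1, +2 at Visit 5.

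A separate sign note for POL is optional. POL change is not an endpoint, and POL response is already defined in words as a decrease in severity.

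The cost is a text edit to the SAP. Data collection and sample size do not change.
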